- Interim analysis for futility and dose adaptation on BICLA response, SRI response, ACR28 and some SLE biomarkers (such as auto-antibodies, complement levels, etc.) with possible exploratory exposure response analysis, will be performed when approximately 30 subjects per arm have reached Study Day 85 (12 weeks), including subjects from Part 1 and Part 2, of treatment or have discontinued prior to reaching study Day 85. Analysis will be performed by an unblinded Sponsor team, while maintaining blind at the site and subject level. Based on the results, the dose levels and sample size may be modified.
- Ongoing assessment of safety will be performed by an independent Data Monitoring Committee (DMC) and an internal unblinded safety monitoring team. Both entities may make recommendations to the Sponsor regarding conduct of study and dose adjustment based on safety observations.

Following interim analyses and DMC reviews, dose arm(s) may be modified based on the results, as follows:

- If one or more arms are added, future randomizations will include the new arm(s).
- If one or more arms are dropped for safety reasons, randomization into that arm will be terminated and all subjects currently randomized to that or those arm(s) will be discontinued from receiving study medication.
- If one or more arms are dropped due to inadequate RO, there will be no new randomizations into that dose arm; subjects currently randomized may continue at the Investigator discretion.

The **long-term extension (LTE) period** is optional and will include eligible subjects who have completed Day 169 (week 24) of treatment and consent to participate. This period of the study will remain blinded but will no longer have a placebo arm. Eligible subjects will remain on their

originally-assigned dose arm, unless they were on the placebo arm during the short-term period. Placebo-arm subjects will be re-randomized into one of the existing active arms at Day 169 (24 weeks). Re-randomization of the placebo subjects will be done by IVRS and only the unblinded pharmacist/drug preparer will know the new randomization arm. The LTE will remain blinded to the study team and study personnel.

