8.2 Populations for Analyses

- All Enrolled Subjects, defined as all subjects who sign an informed consent;
- All Randomized Subjects, defined as all subjects who are randomized to a treatment;
- All Treated Subjects, defined as all subjects who receive at least one dose of study treatment;
- Biomarker Analysis Population, defined as all subjects that receive any study medication and have at least 1 post-treatment biomarker measurement.
- Pharmacokinetic Population, defined as all subjects who receive any study medication and have any available concentration-time data.
- Immunogenicity Population, defined as all subjects who receive study drug and have at least 1 post treatment immunogenicity measurement.

All subjects who receive at least one dose of study treatment (all treated subjects) will be included in the safety analysis population and the efficacy analysis population. However, the subjects from Part 1 who are randomized to a treatment arm that is discontinued based on the Part 1 Safety/RO analysis will be excluded from the efficacy analysis. More details will be provided in the statistical analysis plan.

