### **6.3 Populations for Analyses**

- All Enrolled Subjects: All subjects who signed an informed consent.
- All Randomized Subjects: All subjects who are randomized to a treatment.

- Modified Intent-to-Treat (MITT) Analysis Population: All randomized subjects who have received at least one dose of the study medication. Subjects will be grouped according to the treatment to which they were randomized by IVRS at the start of the study. The MITT analysis population will also be referred to as “All Randomized and Treated Subjects”.
- As-Treated Analysis Population: All Subjects who have received at least one dose of study medication. Subjects will be grouped according to the treatments to which they are randomized, except in cases where a subject receives a different treatment for the entire course of short term period. In this case, the subject will be analyzed and presented by the treatment they actually received.
- Efficacy Analysis Population: This is a subset of the MITT Analysis Population where the subjects from Part 1 who are randomized to a treatment arm and discontinued based on the Part 1 Safety/RO analysis are excluded. All efficacy results that involve statistical comparison or modeling will be based on this analysis population unless otherwise specified.
- Biomarker Analysis Population: All subjects who receive any study medication and have at least one post-treatment biomarker measurement.
- Pharmacokinetic Population: All subjects who received BMS-931699 and have any available concentration-time data.
- Immunogenicity Population: All subjects who receive any study medication and have at least one post treatment immunogenicity assessment.

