**Table 7.1-1: Planned Efficacy Analyses**

Measure of Interest (Primary and Secondary Efficacy Endpoints):	Analysis Method
Counts]	

The Chi-square tests will be used to compare the BICLA response rates at Day 169 between each of the active treatment arms and the placebo arm. The Chi-square p-value will be provided for each comparison between the active treatment and the placebo arm. In addition, the difference of the response rates between each active treatment and the placebo arm will be estimated and their corresponding 90% confidence interval will be calculated. No adjustment will be made for multiplicity.

For each of the binary endpoints, the estimate and its corresponding 90% confidence interval will be calculated for the difference of the proportions between each active treatment arm and the placebo arm at the specified visit, similar to the primary analysis except no p-values will be provided.

The construction of confidence intervals for binary variables will be based on normal approximation if the number of the events in each individual treatment arm is at least 5. Otherwise, confidence interval using an exact method will be provided. The exact confidence intervals for binary variable within treatment group and between treatment groups will be constructed.

For each of the continuous endpoints, the mixed model will be fit with treatment, visit, and treatment-by-visit interaction as the fixed effects and measurements within each subject as the repeated measurements. The baseline value will be added into the model as a covariate if necessary. Based on the mixed model, the estimate and 90% confidence interval will be calculated for the difference between each active treatment and the placebo at each specified visit.

The results will be presented by the following grouping scheme in different periods, unless otherwise specified.

- **Pre-treatment period**: Only one group: All enrolled subjects.
- **Short-term period (ST)**: The results will be presented by treatment groups.

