### **7.5.2 Secondary Efficacy Endpoints in the Short-term Period**

For each of the binary endpoints (SRI(X) etc.), the estimate and its corresponding 90% confidence interval will be calculated for the difference of the proportions between each active treatment arm and the placebo arm for each applicable visit, similar to the primary analysis except no p-values will be provided.

For each of the continuous endpoints (BILAG-2004, SLEDAI, MDGA, CLASI, etc.), the mixed model will be fit with treatment, visit, and treatment-by-visit interaction as the fixed effects and measurements within each subject as the repeated measurements. The baseline value will be added into the model as a covariate if necessary. Based on the mixed model, the estimate and 90% confidence interval will be calculated for the difference between each active treatment and the placebo at each specified visit. No p-values will be provided. In addition, Descriptive summary statistics of mean change from baseline and 90% confidence interval for each treatment arm will be provided. The missing data in continuous measures will be handled via utilization of mixed model procedure in SAS.

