## 7.10 Interim Analyses

### 7.10.1 *Interim Safety/RO Analysis at Day 29*

When at least 6 patients per treatment arm have either reached Study Day 29 or discontinued, an interim analysis (IA) for safety and RO will be performed. The safety analysis will focus on incidence and severity of all adverse events (AEs), serious AEs and pre-established Events of Special Interest such as infection AEs and any other safety analysis requested by DMC. A separate document, DMC charter, describes the scope of these analyses. For RO: the median RO at Day 29 for each treatment arm will be calculated. Based on the results of this interim analysis, a decision will be taken regarding the doses that will be carried forward into Part 2 of the study. Specifically, dosing regimens originally included in Part 1 may be discontinued and/or new dosing regimens may be added according to the following criteria:

Safety:

The DMC in conjunction with an unblinded internal monitoring team (The details of the members are provided in [Section 2.3.2](#)) may require one or more doses to be discontinued if stopping criteria are met or other safety signals arise that the Medical Monitor and/or DMC consider of sufficient concern.

Receptor Occupancy:

- If median RO of any dose is <20%, the sponsor may consider dropping that dose
- If the median RO for all doses is >90% the sponsor may consider adding or replacing a dose in Part 2 of the study to ensure an adequate pharmacodynamic range (dose not to exceed 12.5 mg weekly)

Dose decrease and/or reduction of frequency of administration may also be considered if RO results fall outside the parameters indicated above. This adjustment may occur for safety reasons or in case unforeseen RO profiles observed in SLE patients. The decision to adjust dose and/or frequency will be taken after review of the data by the clinical team. Any decision related to safety reasons will be taken in conjunction with DMC recommendations.

RO analysis in interim analyses 1 will be done by a Pharmacokinetic scientist or a Pharmacometrics analyst. If dose/doses are adjusted based on this RO analysis, then the interim analyses results may be included in CSR as an appendix.

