#### **7.11.6 Analysis for the PK Sub-Study**

As specified in the amendment 9 of the protocol, participation for PK sub-study is voluntary. While there is no minimum required number of subjects, every effort will be made to enroll approximately 4 subjects/arm in the ST study (ie approximately 20 subjects total) and approximately 6 subjects/arm in the LTE (ie approximately 30 subjects total). This sample size is expected to provide sufficient data to adequately estimate PK parameters for lulizumab in this patient population. Subjects will be asked to read, understand, and sign an informed consent form designed for the purpose of collecting the additional PK/RO samples.

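### SAP 6.3 words the Part 1 exclusion by subject where Protocol 8.2 words it by arm, so if an arm is dropped after Part 1 the two rules can give different efficacy populations

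*SAP*

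**What the plan says.** **Protocol 8.2 (arm-level rule).** All treated subjects enter the efficacy population, except that Part 1 subjects "randomized to a treatment arm that is discontinued based on the Part 1 Safety/RO analysis will be excluded from the efficacy analysis". The section leaves further detail to the SAP.

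**SAP 6.3 (subject-level wording).** The Efficacy Analysis Population is the MITT population from which "subjects from Part 1 who are randomized to a treatment arm and discontinued based on the Part 1 Safety/RO analysis are excluded". The same entry makes this the default population for every efficacy result that involves a comparison or a model. SAP 7.5 and 7.5.1 apply it to the efficacy analyses and to the primary BICLA test.

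**What happens to subjects when an arm is dropped (Protocol 3.1, repeated in SAP 2.1).** After a safety drop, everyone currently in the arm is taken off study medication. After a drop for inadequate RO, the arm only closes to new randomization, and "subjects currently randomized may continue at the Investigator discretion".

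**The Day 29 analysis (SAP 7.10.1).** It acts on regimens: "dosing regimens originally included in Part 1 may be discontinued". It is triggered when at least 6 patients per arm "have either reached Study Day 29 or discontinued", so it can include subjects who have already left. A median RO below 20% permits a drop but does not require one.

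**The concern.** The two sentences differ in what has to be discontinued: the arm in the protocol, the subject in the SAP. An RO drop is the case in which an arm can be discontinued while its subjects are not.

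Under the literal SAP wording, membership of the primary efficacy population would then depend on a decision taken after randomization. Subjects stopped because of the RO result would be removed, although they would otherwise count as BICLA non-responders under SAP 7.5.1 and 8.1.1. Subjects chosen to continue would stay. A dose closed at Part 1 would still receive a Day 169 comparison with placebo, on a small selected group. Under the protocol rule it would receive none.

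**Working it through.** **1. The plan's own power figures.** Inputs from SAP 5 and Protocol 8.1: n = 70 per arm, one-sided alpha 0.05, continuity correction, placebo rate 25%.

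Power = Φ[(d − 1/n − 1.645·se0)/se1], where se0 = √(2·p̄(1−p̄)/n), se1 = √((p1(1−p1)+p2(1−p2))/n), and p̄ is the mean of the two rates.

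- 50% vs 25%: (0.25 − 0.0143 − 1.645 × 0.0818)/0.0791 = 1.28, power 0.900 (exact enumeration 0.898; stated at least 89%).
- 45% vs 25%: (0.20 − 0.0143 − 1.645 × 0.0806)/0.0788 = 0.67, power 0.750 (exact 0.747; stated 74%).

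Both are reproduced. They concern pairs of arms that are kept. A dropped arm enters neither side of such a pair, so the choice of rule does not alter them.

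**2. Size of a dropped arm.** Part 1 has about 6-10 patients per arm and at most 50 in all (SAP 2.1). Part 2 starts only after the Part 1 analysis is complete. An arm dropped at that point therefore holds Part 1 subjects only: m = 6 to 10.

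**3. Who is excluded.** Split the arm as m = s + k + e, where s were stopped because of the analysis, k continue, and e left earlier for another reason.

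| Rule | Excluded | Kept |
|---|---|---|
| Protocol 8.2 | m | 0 |
| SAP 6.3, literal | s | k + e |

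The rules differ by k + e = m − s subjects.

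- RO drop: s can be anything from 0 to m, so the difference is 0-6 for m = 6 and 0-10 for m = 10. Against the planned 350, the upper ends are 6/350 = 1.7% and 10/350 = 2.9%.
- Safety drop: everyone still on drug is stopped, so k = 0 and the difference is e alone.

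**4. What the literal rule does to the dropped arm's rate.** Let r be the responders among the k who continue. Those who stopped or left early count as non-responders. The literal rule gives r/(k + e); the rate over all Part 1 subjects of the arm would be r/m. With m = 10, k = 5, e = 0 (assumed), the first is 10/5 = 2 times the second.

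**5. How little such a comparison could show.** Assume all m continue, with 50% response against 25% in 70 placebo subjects. The normal-approximation 90% half-width is 1.645·√(0.25×0.75/70 + 0.5×0.5/m).

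| m | Half-width | Exact power, corrected test |
|---|---|---|
| 6 | 0.35 | 0.26 |
| 8 | 0.30 | 0.32 |
| 10 | 0.27 | 0.37 |

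The half-widths are a rough guide only, because SAP 7.1 uses an exact interval when an arm has fewer than 5 events.

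**6. Retained arms.** Each primary chi-square test uses one active arm and placebo, so none changes. For continuous endpoints, "the mixed model will be fit with treatment, visit, and treatment-by-visit interaction as the fixed effects". An extra small arm in that joint fit would contribute to the shared covariance, so retained-arm estimates could move slightly. The documents give no basis for a figure.

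**The case against.** The strongest reply is that the SAP means the arm. The Day 29 analysis decides about regimens, not individuals. Being randomized to an arm is already true of every MITT subject, so that phrase adds nothing if the clause is read by subject. The protocol rule is unambiguous, and the SAP revision history records no change to the efficacy population. This stands as evidence of a slip. It does not remove the problem, because Protocol 8.2 defers to the SAP for detail and the SAP sentence is the one that would be programmed.

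It can also be said that after an RO drop stopping is the investigator's decision, so strictly nobody is discontinued because of the analysis. That takes s towards 0 and makes the gap between the rules larger.

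Four stronger readings are tempting and are not supported:

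- *The populations will differ.* They differ only if an arm is dropped and at least one of its subjects was not stopped because of the analysis.
- *The dropped dose would be tested on its continuing subjects alone.* Those who left earlier for another reason also stay in, as non-responders.
- *The retained arms' primary results are compromised.* Their pairwise tests are identical under both rules.
- *The point is settled because no arm was dropped.* SAP 6.2 still lists all four doses, and the PK sub-study in SAP 7.11.6 plans about 20 subjects at 4 per arm (20/4 = 5 arms). But the same sentence gives 30/6 = 5 arms for the extension, which has no placebo arm, so this count is not a reliable guide. The documents do not say whether an arm was dropped.

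**Conclusion.** The inconsistency is real and minor. As written, SAP 6.3 sets a different exclusion rule from Protocol 8.2, most likely by a slip of wording, and no other part of the SAP puts it right. If an arm is dropped after Part 1, the efficacy populations can differ by 0 to about 6-10 subjects in that arm. The larger differences arise after an RO drop. The consequence is a possible comparison of an abandoned dose with placebo on a subset chosen after randomization.

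This rests on the literal reading of SAP 6.3, on Part 1 arms of about 6-10, and on an arm actually being dropped, which is optional even when median RO is below 20%.

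**What to change.** In SAP 6.3, change *and discontinued* to *that is discontinued*, so that the condition attaches to the arm as in Protocol 8.2. Add that the exclusion applies whether or not the subject's own treatment continued. Nothing further is needed to remove the discrepancy.

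The cost is one sentence in the SAP, with no protocol amendment and no new data. It should be made before unblinding, so that the choice of rule cannot appear to follow the results.

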## 7 STATISTICAL ANALYSES

### 7.1 General Methods

The table below provides an overview of the efficacy analyses to be performed.

**Table 7.1-1: Planned Efficacy Analyses**

Measure of Interest (Primary and Secondary Efficacy Endpoints):	Analysis Method
Primary endpoint (Binary): BICLA response rate at Day 169	Chi-Square test, one sided p-value will be provided. Point estimates and 90% CI of treatment difference. No multiplicity adjustments.
Binary endpoints : SRI(X) [ X= 4, 5, 6, 8] at Day 85 and Day 169, BICLA response rate at Day 85, CLASI Response at Day 85 and Day 169	Point estimate and 90% CI of response rate, point estimates and 90% CI of treatment difference
Continuous endpoints: CLASI, BILAG-2004, SLEDAI-2K, MDGA, ACR 28 [tender, swollen, and active, (i.e. joints that are both tender and swollen) joint	Mixed model analysis, point estimates and 90% CI for mean change from baseline within treatment groups, point estimates and 90% CI for mean change from baseline between treatment groups (BMS vs. PLA)

**Table 7.1-1: Planned Efficacy Analyses**

Measure of Interest (Primary and Secondary Efficacy Endpoints):	Analysis Method
Counts]	

The Chi-square tests will be used to compare the BICLA response rates at Day 169 between each of the active treatment arms and the placebo arm. The Chi-square p-value will be provided for each comparison between the active treatment and the placebo arm. In addition, the difference of the response rates between each active treatment and the placebo arm will be estimated and their corresponding 90% confidence interval will be calculated. No adjustment will be made for multiplicity.

For each of the binary endpoints, the estimate and its corresponding 90% confidence interval will be calculated for the difference of the proportions between each active treatment arm and the placebo arm at the specified visit, similar to the primary analysis except no p-values will be provided.

The construction of confidence intervals for binary variables will be based on normal approximation if the number of the events in each individual treatment arm is at least 5. Otherwise, confidence interval using an exact method will be provided. The exact confidence intervals for binary variable within treatment group and between treatment groups will be constructed.

For each of the continuous endpoints, the mixed model will be fit with treatment, visit, and treatment-by-visit interaction as the fixed effects and measurements within each subject as the repeated measurements. The baseline value will be added into the model as a covariate if necessary. Based on the mixed model, the estimate and 90% confidence interval will be calculated for the difference between each active treatment and the placebo at each specified visit.

The results will be presented by the following grouping scheme in different periods, unless otherwise specified.

- **Pre-treatment period**: Only one group: All enrolled subjects.
- **Short-term period (ST)**: The results will be presented by treatment groups.

## 7.2 Study Conduct

Relevant protocol deviations, which could have an impact on the primary/key efficacy endpoint, will be identified for all subjects who are randomized and receive study medication during the double-blind period. Details of relevant protocol deviations are provided in [Appendix 1](#).

All subjects with relevant protocol deviations that could affect the primary efficacy will be identified prior to database lock and unblinding of treatment assignment. All relevant protocol

deviations will be listed and summarized by treatment group. The subjects identified as relevant protocol deviation will not be excluded from any analysis population described in [Section 6.3](#). If at least 10% of total subjects in all treatment arms in the efficacy analysis population demonstrate relevant protocol deviations, a per-protocol analysis may be performed.

## **7.3 Study Population**

Frequency distributions or summary statistics of data pertaining to subject disposition, demographic characteristics, baseline disease characteristics, and medical history will be tabulated and displayed by treatment group. No statistical test will be carried out for comparison of any baseline measures among treatment groups.

These presentations will be provided by randomized treatment group for the MITT analysis population, unless specified otherwise.

### **7.3.1 Subject Disposition**

The number of subjects enrolled into the study at screening, the number of subjects randomized, the number of subjects entering the short-term period (ST) and the number of subjects who complete the ST period will be summarized by treatment groups. The number of subjects discontinuing from the ST period (subject disposition) will also be summarized, together with the reasons for discontinuation, taken from the CRF status pages. The subject disposition for the ST period will be based on the MITT analysis population.

### **7.3.2 Demography and Baseline Characteristics**

Demographic and baseline disease characteristics will be summarized by randomized treatment group and overall based on the MITT analysis populations. For continuous variables, they will be summarized using means, standard deviations and ranges. The distribution of categorical variables such as gender, race etc. will be summarized by treatment group using frequency and percentage.

Demographic characteristics include the following:

- Age in years
- Weight in kg
- Gender: Male, Female
- Race
- Ethnicity (Hispanic and Non-Hispanic)
- Region (North America, South America, Europe and Asia)
- Stratification [Japan vs. Non-Japan, MMF use (Y/N)]
- 

Baseline clinical characteristics include the following:

- Time from First Diagnosis of SLE (years)
- Tender Joint Counts
- Swollen Joint Counts

- Active (Both Tender and Swollen) Joint Counts
- BILAG classifications and numerical scores
- SLEDAI-2K Score
- CLASI Score
- Physician's global assessment of disease activity (MDGA)
- Subject's global assessment of disease activity (PGA)
- SLICC/ACR damage index
- Total corticosteroid daily dose (prednisone equivalent) at baseline

